There has been a longstanding recommendation for pneumococcal vaccination for PLWH in the United States. PCV13 was recommended for PLWH in 2012 and the uptake in PLWH is higher compared with individuals with other risk conditions [22, 23]; this allows us to examine PCV13 VE in the PLWH population over time. Given the lack of PCV13 VE data in immunocompromised adults, this study was designed to estimate PCV13 VE against pneumococcal disease in PLWH aged ≥ 18 years, overall and, if feasible, at 3, 5, and 7 years after vaccination. In addition to IPD and pneumococcal pneumonia, we will include all-cause pneumonia as a disease endpoint in the analysis, because *S. pneumoniae* is the most common bacterial cause of all-cause pneumonia [24].

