		
Adherence will be measured as 'Proportion of days covered = (Number of days covered by any ART, excluding ritonavir and cobicistat) ÷ (total days)*100'[27] every six months
 
Individuals with >80% of days covered will be classified as 'adherent' and individuals with ≤80% of days covered will be classified as 'non-adherent'[27]
	
	CD4 cell count	Categorized as <200, 200-499, ≥500 cells/mm ³	Baseline and follow-up
	PPSV23 vaccination	NDC and CPT codes listed in Appendix Table 8	Baseline and follow-up
	Annual CD4 laboratory test	
CD4 laboratory tests will be identified by CPT codes listed in Appendix Table 9
 
Individuals who have at least one CD4 laboratory test performed during each year of follow-up
	Baseline and follow-up
	Annual viral load laboratory test	
Viral load laboratory tests will be identified by CPT codes listed in Appendix Table 10
 
Individuals who have at least one viral load laboratory test performed during each year of follow-up
	Baseline and follow-up
	Respiratory virus season	Respiratory virus season occurs between October 1 and April 30	Follow-up
Sensitivity analysis outcome	All-cause pneumonia not associated with HIV	ICD-9-CM or ICD-10-CM codes listed in Appendix Table 11	Follow-up

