9.7. Data Analysis

Cox proportional hazards models will be used to estimate the hazard ratio (HR) for each outcome comparing vaccinated PLWH with unvaccinated (no PCV13) PLWH. To explore potential changes in VE over time, HRs will also be generated during specific time periods (0-3, 3-5, 5-7 years of follow-up) using piecewise Cox regression models, if there is adequate sample size. All models will be adjusted for time-fixed and time-varying covariates of interest using inverse probability of treatment weighting. The time-fixed covariates of interest include sex, age, payor, SVI, previous pneumonia infection, and hospitalization and will be measured during the baseline period. The time-varying covariates include risk factors for pneumonia (alcoholism, asplenia, asthma, chronic heart disease, kidney, liver, and lung diseases, cigarette smoking, diabetes, immunosuppressive conditions and medications, and sickle cell disease), annual physical exams, annual influenza vaccine, hospitalization, opportunistic infections, ART adherence, annual CD4 and viral load laboratory tests, and an indicator for respiratory virus season.

VE will be calculated as 1 minus the estimated HR for each outcome.

We will conduct two sets of analyses for each outcome. In the first set, we will examine the first event for each outcome and in the second set, all recurrent outcome events during follow-up will be included. In the first set of analyses, unvaccinated (no PCV13) PLWH will be followed from index date until the earliest occurrence of the following: outcome, PCV13 vaccination, death, end of health plan enrollment, or end of study period, and vaccinated PLWH will be followed from 14 days after vaccination date, or index date if vaccinated during the baseline period, until the earliest occurrence of outcome, death, end of health plan enrollment, or end of study period. In the second set of analyses unvaccinated (no PCV13) PLWH will be followed from index date until the earliest occurrence of PCV13 vaccination, death, end of health plan enrollment or end of study period and vaccinated PLWH will be followed from 14 days after vaccination date, or index date if vaccinated during the baseline period, until earliest occurrence of death, end of health plan enrollment, or end of study period.

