### 5.2.3. Subgroups and Stratification

*Several stratified analyses will be conducted. PPSV23 is recommended for PLWH and feasibility data provided by Komodo suggest that one in four PWLH who received PCV13 during 2014-2015 also received PPSV23 within two years. Rather than censor or exclude individuals who receive PPSV23, we will calculate PCV13 VE among PWLH who have/have not received PPSV23 before and during the study period. The analysis may also be stratified by the number of PPSV23 doses, e.g. 0, 1, 2+.*

*Feasibility assessments from Komodo indicate that approximately 25% of PWLH have at least one CD4 cell count or percentage laboratory result available. Therefore, we will calculate PCV13 VE among the subset of PWLH who have a CD4 cell count during the baseline period or follow-up, and potentially stratify by CD4 category using the patient's lowest value during the study.*

*Additional VE stratifications by ART adherence during follow-up, year of HIV diagnosis, and age will be assessed for feasibility as well, as these affect patients' immune status and immune reconstitution. Due to possible waning of the VE and different lengths of follow-up by index year, VE stratification by year of HIV diagnosis will be restricted to the first 3 years of follow-up (0 to 1079 days).*

The above subgroup analyses will be conducted if there are sufficient numbers of patients/events to maintain patient de-identification (Section 5.8.3) and where the 95% confidence intervals (CI) for the VE estimates can be expected to exclude zero in the best case scenarios for the analyses, i.e. the highest expected VE estimate, the lowest expected censoring rate and at the maximum follow-up time. Table 5.1 provides precision estimates for IPD and all-cause pneumonia under different numbers of individuals available for the analysis. The following assumptions were used for the estimates:

- 32% of individuals received PCV13
- IPD incidence among PLWH is 183 cases per 100,000 population [1]
- All-cause pneumonia incidence among PLWH is 5,487 cases per 100,000 population
- VE for IPD due to any serotype is 22.5% [2, 3]
- VE for all-cause pneumonia is 15% [4]

- Annual censoring of individuals due to loss to follow-up or death is 4%
- Up to 97 months of follow-up

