### 5.3.2. Covariates

The list of demographic and clinical characteristics considered for descriptive reporting, subgroups and inclusion as covariates in models for generating the propensity scores are provided in Table 5.3. The Komodo Health database will be source of all variables.

Patients will be considered to have a comorbidity or hospitalization during baseline if there was evidence of a diagnosis at any time during the baseline period. Evidence of comorbidities or hospitalization during follow-up will be considered as new diagnoses. Once diagnosed, patients will be considered diagnosed for the remainder of their follow-up. ART adherence during baseline and follow-up will be updated every 6 months (180 days) based on the data collected in that previous timeframe. For baseline annual physical exam and annual influenza vaccine, patients will be considered adherent (coded as 'Yes') if there was evidence of these events at any time during the baseline period. During the follow-up, patients will be considered adherent up to 365 days after the last event date.

For annual CD4 and viral load laboratory tests during baseline and follow-up, patients will be coded as 'Yes' up to 365 days after the last event date. For respiratory virus season during follow-up, patients will be coded as 'Yes' if the observation time is in October, November, December, January, February, March or April.

The baseline period for the assessment of covariates is the six months prior to the index date, i.e., no data prior to six months will be included.

Covariates used at baseline only will be considered time-fixed confounders. Covariates additionally or only used during follow-up will be considered time-varying confounders.

Categories may be collapsed, or covariates may be excluded from the propensity scores if models fail to converge.

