Any hospitalization	Evidence of inpatient claim(s) Yes, No	Descriptive, covariate	Baseline and follow-up
Hodgkin's lymphoma	ICD-9-CM or ICD-10-CM codes listed in Protocol Annex 1.11 Yes, No	Descriptive, covariate	Baseline and follow-up
Opportunistic infections	ICD-9-CM or ICD-10-CM codes listed in Protocol Annex Table 14	Descriptive, covariate	Baseline and follow-up

	Yes, No  Note: In the analysis of all-cause pneumonia, pneumocystis jirovecii pneumonia codes are excluded from the follow-up. In the analysis of candidiasis negative control outcomes, candidiasis infection codes are excluded from the follow-up.		
Antiretroviral treatment (ART) adherence	ART use will be identified by NDC codes listed in Appendix Table 7.2  Adherence will be measured as 'Proportion of days covered = (Number of days covered by any ART, excluding ritonavir and cobicistat) ÷ (total days)*100'[8] every six months  Individuals with >80% of days covered will be classified as 'adherent' and individuals with ≤80% of days covered will be classified as 'non-adherent'[8]. Individuals without ART information will be classified as Missing. As a subgroup, ART adherence will be calculated using the information over the entire follow-up.	Descriptive, covariate, subgroup	Baseline and follow-up
CD4 cell count	Categorized as <200, 200-499, ≥500 cells/mm 	Descriptive, subgroup	Baseline and follow-up
PPSV23 vaccination	NDC and CPT codes listed in Appendix Table 7.9  Yes, No. 0, 1, 2+ doses	Descriptive, subgroup	Before first HIV diagnosis, baseline and follow-up
Annual CD4 laboratory test	CD4 laboratory tests will be identified by CPT codes listed in Appendix Table 7.11  Individuals who have at least one CD4 laboratory test performed during each year of follow-up Yes, No	Covariate	Baseline and follow-up
Annual viral load laboratory test	Viral load laboratory tests will be identified by CPT codes listed in Appendix Table 7.12  Individuals who have at least one viral load laboratory test performed during each year of follow-up Yes, No	Covariate	Baseline and follow-up

Respiratory virus season	Respiratory virus season occurs between October 1 and April 30 Yes, No	Covariate	Follow-up
--------------------------	---	-----------	-----------

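### PPSV23 given before PCV13 is recorded but left out of the weights behind overall VE; the PPSV23 strata do not replace it and lack a stated stop date

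*SAP*

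**What the plan says.** **Weights.** SAP 5.3.2 says that the characteristics considered for description, subgroups and "inclusion as covariates in models for generating the propensity scores are provided in Table 5.3". In that table PPSV23 is used at "Before first HIV diagnosis, baseline and follow-up", but its role is descriptive and subgroup only. Influenza vaccine, annual physical exam and the CD4 and viral load test indicators all carry the role of covariate.

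Protocol 9.7 states: "The time-fixed covariates of interest include sex, age, payor, SVI, previous pneumonia infection, and hospitalization". Its time-varying list runs through comorbidities and ends with "annual influenza vaccine, hospitalization, opportunistic infections, ART adherence, annual CD4 and viral load laboratory tests, and an indicator for respiratory virus season". Neither list names PPSV23. Protocol Table 1 nevertheless places PPSV23 ("NDC and CPT codes listed in Appendix Table 8") under Covariates, measured at baseline and follow-up.

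**Strata.** SAP 5.2.3 and protocol 9.7 choose not to censor or exclude PPSV23 recipients; instead, "we will calculate PCV13 VE among PWLH who have/have not received PPSV23 before and during the study period". The SAP adds an optional split by number of doses. Neither document says when counting of receipt stops.

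**Look-back.** SAP 5.3.2 says of baseline covariates that "no data prior to six months will be included", while the PPSV23 row reaches back before the first HIV code.

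**The concern.** PPSV23 is another vaccine against the same pathogen, and the SAP itself calls it recommended for this population. Protocol section 7 adds: "There has been a longstanding recommendation for pneumococcal vaccination for PLWH in the United States". So some people will plausibly have received PPSV23 before PCV13. If those doses are related both to getting PCV13 and to pneumococcal outcomes, leaving them out of the weights biases overall VE, which is what all three primary objectives ask for.

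The plan accepts the principle elsewhere: influenza vaccine is weighted, and the zoster vaccine analysis in SAP 5.8.12 adjusts for PCV13.

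PPSV23 given after PCV13 is a different matter. SAP 5.8.4 holds the treatment weights constant after PCV13 and the plan keeps PPSV23 recipients in follow-up, so later doses form part of the estimated effect. The SAP does not say so.

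The strata raise a second, smaller question. They classify people partly by what happens after index, and whether that distorts VE depends on a stop date that is not given.

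**Working it through.** **1. Does anything else in the plan bring PPSV23 into overall VE?**
- Weights are regenerated within subgroups (SAP 5.8.4). This does not reach the unstratified estimate.
- Variables with SMD above 0.1 may be added to the outcome model (SAP 5.8.5). The check covers listed covariates, which PPSV23 is not, and adding is optional.
- Absence from the protocol 9.7 lists is weak evidence by itself: the time-fixed list also omits region and index year, which are covariates in SAP Table 5.3. The role column of Table 5.3 is the decisive text.

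**2. Would the strata be run for IPD?** SAP 5.2.3 runs a subgroup only if its best-case CI can be expected to exclude 0. To reproduce Table 5.1, take the standard error from protocol Table 2 (VE 22.5%, 4% censoring, 97 months, CI 11% to 33%):

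SE = ln(0.89/0.67)/(2 × 1.96) = 0.0724

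Scale by √(175,000/n), with limits 1 − 0.775 × exp(±1.96 SE).

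| n | Computed | Table 5.1 |
|---|---|---|
| 58,000 | 0.8% to 39.4% | 1% to 40% |
| 43,000 | −3.2% to 41.8% | −5% to 41% |
| 35,000 | −6.5% to 43.6% | −6% to 44% |

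The table reproduces to within 2 points. A stratum of a quarter of the cohort fails for IPD; passing at 58,000 needs 58,000/175,000 = 33%. The actual stratum sizes are not in the documents: the one-in-four figure covers only people given PCV13 in 2014-2015, within two years.

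**3. How far could overall VE move?** Let p1 and p0 be prior PPSV23 coverage in PCV13-vaccinated and unvaccinated time, and v the PPSV23 effect.

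Shift = (1 − VE) × [1 − (1 − p1·v)/(1 − p0·v)]

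The documents give none of p1, p0 or v. Assume |p1 − p0| = 0.10 with both between 0.05 and 0.35, and borrow the protocol's PCV13 range for v.
- IPD (VE 0, 7.5% or 22.5%): 0.58-0.77 points at v = 0.075; 1.76-2.44 at v = 0.225.
- Example: VE 22.5%, v = 0.225, p1 = 0.25, p0 = 0.15 gives 0.775 × (1 − 0.94375/0.96625) = +1.8 points. Swapping p1 and p0 gives −1.8.
- All-cause pneumonia, v = 0.05 or 0.15, VE 0 to 15%: smallest 0.85 × 0.005/0.9975 = 0.4 points; largest 0.015/0.9475 = 1.6.
- Wider assumption, v = 10-50%, true VE 0: coverage 25% versus 5-15% gives +1.0 to +10.3 points; 15% versus 25% gives −1.0 to −5.7; equal coverage gives 0.

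**4. Strata.** Inputs from the documents: all-cause pneumonia 5.487%/year, IPD 0.183%/year, 32% receiving PCV13, PPSV23 after PCV13 at −ln(0.75)/2 = 0.144/year. Assumed: no effect of either vaccine, PPSV23 before PCV13 at 0.02-0.30/year, and 0 or 20% holding PPSV23 at index. A four-state model (PCV13 no/yes by PPSV23 no/yes) over 97 months gives, for true VE 0:

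| Counting of receipt | Bias in VE (points) |
|---|---|
| To end of enrolment, unrelated to outcome | 0 |
| To end of enrolment, 5% of episodes prompt PPSV23 (assumed) | 'Have': +5 to +17 at 0.02/year; +2.5 to +6.9 at 0.05; +0.7 to +1.7 at 0.10; 0 at 0.144; −0.4 to −1.6 at 0.20-0.30 |
| To end of enrolment, IPD, 8% fatality ends capture | 'Have not': −0.7 to −3.3 at 0.02-0.10; +0.9 to +7.0 at 0.20-0.30. 'Have': within 1 |
| Only to first event | 'Have not': −7 to −35 at 0.02-0.10; 0 at 0.144; +8 to +33 at 0.20-0.30 |

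A separate simulation (3 million people per scenario, 10% holding PPSV23 at index, 0.02-0.05/year before PCV13) agrees for counting to the first event: −17.1 to −22.8 in 'have not'. Counting to end of enrolment gave values within about 1 point of 0.

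**The case against.** **The weights.** The shift is small beside IPD precision: 0.6-2.4 points against a best-case interval of 11% to 33%. No coverage gap or PPSV23 effect is documented, and influenza vaccine, physical exams, ART adherence and laboratory testing, already weighted, may narrow any gap. All of this stands and is why no size or sign is claimed. It matters less for all-cause pneumonia, where protocol Table 3 gives 13% to 17% and the borrowed range gives 0.4-1.6 points. It also does not justify omitting a relevant variable that is already held.

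**The strata.** A reader might infer that the strata sort people by receipt after follow-up starts rather than by status at index, and that stratum VE could be wrong by 35 points. The text does not support this. It counts receipt before as well as during the study period, so earlier doses classify people too. The largest figures require counting to stop at the first event. SAP 5.8.4 and Appendix 7.2.1 end the first-event records and weights there, but do not say that strata are built that way. The ordinary reading runs to the end of study or enrolment, where bias is 0 if PPSV23 is unrelated to the outcome.

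**Index strata as the remedy.** A reader might also infer that strata fixed at index are unbiased throughout. That follows only if PPSV23 has no effect. With a 7.5-22.5% PPSV23 effect, PCV13 null and 4% censoring, apparent IPD VE in the index 'no' stratum is +0.4 to +5.3 points at 0.02-0.10/year and −0.8 to −2.9 at 0.30/year, because PPSV23 uptake differs after PCV13. Index strata also answer a partly different question: modification by prior PPSV23. They belong beside the planned strata, not in their place.

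**Conclusion.** The main point holds. PPSV23 given before PCV13 is captured, has no covariate role in the SAP, and is a potential confounder of overall VE that nothing else in the plan adjusts for. The SAP role and the protocol's Covariates listing disagree. The strata do not close the gap and may fall away for IPD.

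The size is conditional: about 0.6-2.4 IPD points per 10-point gap in prior coverage, in either direction, on a PPSV23 effect borrowed from the protocol's PCV13 range. With equal coverage it is 0. The documents establish neither a direction nor that the bias is material.

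The strata point is one of specification, not demonstrated bias. The definition uses post-index information and leaves the stop date open. Results can be distorted if episodes prompt PPSV23, if death ends capture, or if counting stops at the first event; the documents establish none of these as what will happen in the strata.

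**What to change.** 1. Give PPSV23 the role of covariate in SAP Table 5.3, in line with protocol Table 1, and name it in protocol 9.7.
2. Add PPSV23 before index as a time-fixed covariate. Under SAP 5.8.4 and 5.8.7 it then enters the weight numerators and denominators and the outcome model.
3. Add lagged PPSV23 received to date, up to PCV13, to the IPTW and IPCW denominators, and include PPSV23 in the balance checks.
4. Confirm that the PPSV23 row's use of data before the first HIV code overrides the six-month look-back rule.
5. State that PPSV23 given after PCV13 is part of the estimated effect.
6. For the planned strata, state that receipt is not cut off at the outcome, and label them descriptive. Add strata by PPSV23 status at index, noting that these assess modification by prior PPSV23.

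**Cost.** SAP and protocol wording and reprogramming, with data already held. Some prior doses will be missed, because claims start on January 1, 2014 and no enrolment before the first HIV code is required. The index 'yes' stratum may be too small for IPD: at an assumed 20% (0.20 × 175,000 = 35,000), Table 5.1 gives −6% to 44% for IPD, which fails the SAP's rule, and 9% to 20% for all-cause pneumonia, which passes.

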weights after vaccination will be constant. Time-varying covariates will be lagged, i.e., within each 30-day (or 90-day for RZV) interval the vaccination status will be the status at the end of the interval, whereas the values for the covariates will be from the end of the previous interval. Cox proportional hazards models will be used to model the associations between vaccination status and the numerators and denominators.

It is possible that censoring may be informative, with patient characteristics associated with loss to follow-up. Therefore, patients who are censored may have different risks of the study outcomes than patients who are not censored. Inverse probability of censoring weighting (IPCW) will also be generated during the follow-up using the above methods for IPTW. These weights will be multiplied by the IPT weights to produce a new set of weights [9].

Distributions of the IPT, IPC and IPT\*IPC weights will be summarized by vaccination status. In the presence of extreme/outlier weights, stabilized weights may be truncated at the 1st and 99th percentiles for use in the Cox models for the outcomes. Although there is no formal definition of an extreme weight, the need for truncation will be judged based on the distributions and the potential effect on the interpretation of results [9].

Weights for first and recurrent events will be generated separately in datasets created for each study outcome; however, all weights will be derived without assessing their impact on the VE estimates. Weights will also be generated again in each of the subgroups. The weights will be generated using the *ipwtn* function within the *ipw* R package [10]. Example R code is provided in Appendix 7.2.

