#### **5.8.8. Assessment of Residual Confounding**

*Residual confounding of our VE estimates due to inadequate control for health care seeking behavior and immune status in our analyses will be explored. To do so, we will employ a negative control exposure and a negative control outcome. Potential negative control exposures include vaccinations that are recommended for PLWH but would not be expected to have any protective effect against the pneumonia outcomes of interest. We plan to use recombinant zoster vaccine (RZV) as the negative control exposure. Current US clinical guidelines recommend that PLWH be offered RZV vaccination. Therefore, we will develop a*

*model for our study population in which the exposure is at least one dose of RZV and the outcomes are our primary outcomes of interest. If residual confounding does not exist, RZV would not have an effect on the pneumonia outcomes. However, if the analysis demonstrates that RZV protects against these outcomes, this suggests the presence of residual confounding. Patients who have evidence of RZV during the six-month baseline period will be excluded from the negative control exposure analysis.*

*Similarly, potential negative control outcomes are outcomes that share the same sources of biases as the primary outcomes in our study population but are not causally-related to PCV13 vaccination. For example, immune status is an important predictor of pneumonia outcomes among PLWH, but we will be missing CD4 laboratory values for most of our study population. In order to detect potential residual confounding by lack of control for immune status, a potential negative control outcome could include a more common AIDS defining illness such as candidiasis. Again, if no residual confounding exists, PCV13 vaccination would have no effect on the occurrence of the negative control outcomes. However, if the results suggest that PCV13 vaccination prevents the negative control outcomes, residual confounding may exist.*

If the negative control outcome analysis indicates residual confounding, the results of the main outcomes may be additionally reported after correcting for the bias [12].

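### In the CD4 subset the planned weights adjust for having had a CD4 test, not for the CD4 value, so by design that analysis does not balance the vaccination groups on CD4

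*SAP*

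**What the plan says.** SAP 5.2.3 and Protocol 9.7 plan a VE estimate in people with CD4 data: "we will calculate PCV13 VE among the subset of PWLH who have a CD4 cell count during the baseline period or follow-up". The feasibility figure is about 25% of the cohort, but it counts people with either a cell count or a percentage result. Stratification by CD4 level is optional: "potentially stratify by CD4 category using the patient's lowest value during the study".

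SAP Table 5.3 defines the CD4 cell count as "Categorized as <200, 200-499, ≥500 cells/mm" (cubed), measured at baseline and in follow-up, with the role "Descriptive, subgroup". A separate row, annual CD4 laboratory test, has the role of covariate and is defined by testing alone: "Individuals who have at least one CD4 laboratory test performed during each year of follow-up". Viral load is handled in the same way.

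The list of time-varying adjustment variables in Protocol 9.7 ends with "ART adherence, annual CD4 and viral load laboratory tests, and an indicator for respiratory virus season"; the CD4 value is absent. Protocol Table 1 nevertheless places CD4 cell count in its covariate block, at baseline and follow-up.

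SAP 5.8.4 says "Weights will also be generated again in each of the subgroups", with no CD4 term added for the CD4 subset. SAP 5.8.8 explains why this matters: "immune status is an important predictor of pneumonia outcomes among PLWH, but we will be missing CD4 laboratory values for most of our study population".

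**The concern.** The plan identifies immune status as an important predictor of pneumonia and accepts that it is mostly unmeasured. The CD4 subset is where it is measured, yet the measurement enters neither the weights nor the outcome model. Two people with the same testing history, one with a CD4 of 100 and one with 700, are exchangeable as far as the CD4 terms in the model go.

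As specified, the subset VE shows whether VE differs among people with laboratory data. It does not show how far differences in CD4 between vaccinated and unvaccinated time contribute to the main estimate. The optional strata do not fill this gap, because the lowest value over the whole study may be recorded after vaccination or after the pneumonia being counted.

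**Working it through.** **1. Subset size and the plan's own precision.** 25% of 175,000 is 43,750, which matches the N/4 row (43,000) of SAP Table 5.1. That row gives a 95% CI of -5% to 41% for IPD (VE 22.5%) and 10% to 20% for all-cause pneumonia (VE 15%).

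To reproduce it, use SE(log HR) = 1/√(D·v), where D is the number of events. Take v from Protocol Table 2 (IPD, VE 22.5%, 97 months, 4% censoring, 1,452 events, CI 11% to 33%):

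- SE = ln(0.89/0.67)/(2 × 1.96) = 0.0724
- v = 1/(1,452 × 0.0724²) = 0.131

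Scale the events by 43,000/175,000 and use CI = 1 − (1 − VE)·exp(±1.96·SE):

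- IPD: 1,452 × 43/175 = 357 events, SE 0.146, CI -3.2% to 41.8% (plan: -5% to 41%).
- All-cause pneumonia: 38,176 × 43/175 = 9,380 events, SE 0.0285, CI 10.1% to 19.6% (plan: 10% to 20%).

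Both agree to within 2 points, which is reasonable for 100 to 200 simulation runs.

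**2. Which outcomes are affected.** SAP 5.2.3 runs a subgroup only if the best-case 95% CI is expected to exclude zero. At N/4 IPD fails this condition and all-cause pneumonia passes it. The point therefore applies mainly to all-cause pneumonia and other common outcomes.

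**3. Possible size of the bias.** The documents give no CD4 distribution by vaccination status and no hazard ratio for low CD4. The following inputs are assumptions: CD4 below 200 in 7% v 10%, or 10% v 15%, of the two groups, with a hazard ratio R of 2 to 4. With p₁ the share in vaccinated time and p₀ the share in unvaccinated time, the bias factor on the HR is [1 + p₁(R−1)]/[1 + p₀(R−1)]. Apparent VE when the true VE is 0:

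| p₁ v p₀ | R = 2 | R = 3 | R = 4 |
|---|---|---|---|
| 7% v 10% | 1.07/1.10 = 0.973 → 2.7% | 1.14/1.20 = 0.950 → 5.0% | 1.21/1.30 = 0.931 → 6.9% |
| 10% v 15% | 1.10/1.15 = 0.957 → 4.3% | 1.20/1.30 = 0.923 → 7.7% | 1.30/1.45 = 0.897 → 10.3% |
| 10% v 7% | 1.10/1.07 = 1.028 → -2.8% | 1.20/1.14 = 1.053 → -5.3% | 1.30/1.21 = 1.074 → -7.4% |
| 15% v 10% | 1.15/1.10 = 1.045 → -4.5% | 1.30/1.20 = 1.083 → -8.3% | 1.45/1.30 = 1.115 → -11.5% |

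If the true VE is 15%, 10% v 15% gives an apparent 18.7%, 21.5% and 23.8%; 15% v 10% gives 11.1%, 7.9% and 5.2%. These figures treat no proxy as adjusted, so they sit at the upper end for the inputs chosen.

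**4. Whether adjusting for CD4 removes it.** A small simulation used 43,000 people, time-varying vaccination, 15% with CD4 below 200, R = 2 to 4, and a vaccination rate at low CD4 of 0.5, 0.75 or 1.33 times the rate otherwise, with 60 runs per setting. Without CD4, a true VE of 0 appeared as -3.6% to 15.0%, and a true 15% as 11.9% to 27.6%. Stratified on CD4, the results were -0.6% to 0.4% and 14.4% to 15.5%. This is an ideal case, with CD4 fixed and fully observed.

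**The case against.** Several points on the other side have force.

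- **Imbalance is not shown.** A reader might infer that the groups are unbalanced on CD4. The documents support neither that nor a direction. What stands is that nothing in the plan balances them on it.
- **Proxies are adjusted.** ART adherence, opportunistic infections, hospitalization, and immunosuppressive conditions and medications are in the weights. It would therefore be too strong to say that the subset carries the same confounding as an analysis with no control for immune status. One proxy is weaker here, though: for all-cause pneumonia, SAP Table 5.3 removes pneumocystis codes from the follow-up opportunistic-infection covariate, while SAP Table 7.4 counts pneumocystosis in that outcome.
- **Imbalance could be seen and acted on.** SAP 5.8.9 repeats the descriptive tables in the subgroups, so CD4 would be tabulated by vaccination status at the end of baseline. SAP 5.8.5 allows variables with an SMD above 0.1 to be added to the outcome model. The assumed imbalances would qualify: 0.03/√[(0.0651 + 0.09)/2] = 0.11 and 0.05/√[(0.1275 + 0.09)/2] = 0.15. But the rule is discretionary, it is written for the covariates, and CD4 does not have that role in the SAP. Tabulating CD4 does not adjust for it.
- **The plan gives the subset no confounding role.** It assigns residual confounding to the negative controls, with candidiasis suggested for immune status. That is correct, and nothing says that a similar subset VE would be read as reassurance. The gap is a missed direct check, not a false claim.
- **Precision.** A reader might take the N/4 interval as proof that the subset could detect a change after CD4 adjustment. Table 5.1 gives the precision of one VE, not of the difference between two estimates in the same people.

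**Conclusion.** The point holds in this form. In the CD4 subset the weights adjust for testing and not for the CD4 value, and the only other CD4 control is an optional stratification on a value that may follow vaccination or the outcome. Protocol Table 1 and SAP Table 5.3 also differ on the role of CD4.

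Under the assumed prevalences and hazard ratios, and before any allowance for adjusted proxies, the bias is roughly 3 to 10 VE points in either direction (11.5 at the reverse extreme). The plan expects an all-cause pneumonia VE of 5% to 15%. The true size and sign cannot be derived from the documents. The subset may also be smaller than 43,000, because the 25% includes people with only a CD4 percentage.

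It would go too far to conclude that the main VE is confounded by CD4, or that the subset result will mislead. The supported conclusion is that the plan holds the data for a direct check on a confounder that it names, and does not specify that check.

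**What to change.** 1. Reconcile Protocol Table 1 with SAP Table 5.3, and add to the CD4 cell count row the role of covariate within the CD4 subset.
2. In that subset, keep the planned index date. Add the most recent lagged CD4 category, with a level for not yet measured, to the IPTW and IPCW denominators. Add the baseline CD4 category, with a level for not measured, as a time-fixed covariate; under SAP 5.8.4 and 5.8.7 it then also enters the numerators and the outcome model.
3. Alternatively, restrict to people with a baseline CD4 result and adjust for it.
4. Report VE in the same people with and without CD4 in the weights, as a sensitivity check on immune-status confounding alongside the negative controls.
5. If CD4 strata are shown, define them by baseline CD4, which precedes every counted outcome, and not by the lowest value during the study.

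Starting follow-up at the first CD4 result is not advised. It changes the population and admits people already vaccinated, whose vaccination cannot then be weighted on CD4.

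Cost: SAP wording, one extra weight run on data already held, and somewhat more variable weights. With the restriction to a baseline CD4, the cost is a smaller sample and a wider CI; the documents do not allow that loss to be quantified.
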